### **3.5.9. Physician Withdrawal Checklist (PWC-20)**

*The PWC-20 is a 20-item reliable and sensitive instrument for the assessment of BZ-like discontinuation symptoms. It correlates extremely highly with the PWC-35, its parent scale ( $r=0.980$ ). Since most items are also complaints commonly reported by patients as symptoms of anxiety, it is not surprising that the PWC-20 and the Hamilton Anxiety Rating Scale (HAM-A) correlate highly ( $r=0.80$ ) with each other. Therefore, a combination of symptoms and time course, not type of symptoms alone, best differentiate between discontinuation symptoms of rebound/withdrawal and return of anxiety. Discontinuation symptoms occur early and disappear rather swiftly, depending upon speed of taper, daily medication dose, and drug elimination half-life.*

Determine the number of subjects with each symptom present (eg, mild or higher severity) and categorize each subject by severity (eg, mild, moderate, and severe). Only non-missing items are considered in summary presentations, and will establish the denominator.

The total PWC-20 score is the sum of 20 item-scores and ranges between 0 and 60. The higher score indicates more frequent/severe symptoms. If more than 5 of the 20 individual items are missing then the total PWC-20 score will be set to missing; otherwise, the total PWC-20 score will be imputed as follows: sum of the non-missing item scores X (total number of items)/ (number of items non-missing).

## **4. ANALYSIS SETS**

Data for all subjects will be assessed to determine if subjects meet the criteria for inclusion in each analysis population prior to unblinding and releasing the database and classifications will be documented per standard operating procedures.

#### 4.1. Full Analysis Set

*All efficacy analyses will be based on the Full Analysis Set (FAS) which is defined as all subjects who are randomized to the study, receive at least 1 dose of study medication, and have a baseline and at least one post-baseline MDS-UPDRS score Part III. The FAS is the primary population for efficacy.*

The FAS subjects will be analyzed according to their randomized treatment regardless of the actual treatment they received.

#### 4.3. Safety Analysis Set

The safety analysis set will include all patients who received at least one dose of PF-06649751 or placebo. The safety analysis set is the primary population for treatment administration/compliance and safety.

All subjects who receive at least one dose of study medication will be classified according to the actual study treatment received. A randomized but not treated subject will be excluded from the safety analyses. A treated but not randomized subject or a randomized but took incorrect treatment subject will be reported under the treatment actually received.

CCI  
[Redacted]  
[Redacted]  
[Redacted]

CCI

## 5. GENERAL METHODOLOGY AND CONVENTIONS

See the Interim Analysis Plan (IAP) and Internal Review Committee (IRC) Charter for details on any unblinding for the interim analysis.

The blind for the study will be broken and the final analysis of the study data will be conducted once the last remaining subject has completed the study or is withdrawn from the study prior to completion, all data have been entered into the database, all data issues resolved, the per protocol population has been determined, and the database has been locked.

### 5.1. Hypotheses and Decision Rules

The sample size is based on the primary endpoint, the change from baseline in the MDS-UPDRS score Part III at Week 15. The comparisons will be of PF-06649751 against placebo, and the decision criteria for efficacy are given below:

- C1: At least 50% confident that PF-06649751 effect is 3.6 units better than placebo.
- C2: at least 95% confident that PF-06649751 effect is better than placebo effect.

Better is defined as a reduction in the MDS-UPDRS score Part III.

### 5.2. General Methods

Descriptive summaries for the efficacy, safety, baseline, and other endpoints will be displayed by treatment group:

- PF-06649751; and
- Placebo

#### 5.2.1. Analyses for Binary Data

Analyses for any binary data output will show the number and percentage of subjects in each response category, and the response rate and its 90% confidence interval (CI) will be calculated. The confidence interval of the response rate will be calculated based on the method of Agresti-Coull. Also, the difference of the response rates (with 90% CIs) between each PF-06649751 treatment group and placebo group will be presented.

#### 5.2.2. Analyses for Continuous Data

Descriptive statistics n, mean, median, standard deviation, minimum, and maximum will be used to summarize the endpoints. The differences of each PF-06649751 treatment versus the placebo group with 90% confidence intervals from the fitted model will be reported.

### 5.2.2.1. Restricted Maximum Likelihood (REML)-based Mixed Model for Repeated Measures (MMRM)

The primary analysis will utilize a restricted maximum likelihood (REML)-based mixed model for repeated measures (MMRM). The response variable in the model will be the change from baseline to each post baseline visit, and the following fixed effects will be included in the model:

- Treatment (with 2 levels: PF-06649751 and placebo), a binary factor.
- Visit, a categorical factor.
- Treatment-by-visit interaction.
- Baseline MDS-UPDRS score Part III, a continuous covariate.
- Baseline-by-visit interaction.
- Geographic region (stratification factor).
- Concurrent anti- PD med Yes/No at randomization (stratification factor).

An unstructured variance-covariance structure will be used to model the within-subject errors. In the unlikely event that the computational algorithm fails to converge, the following structures will be executed in the order specified (essentially in decreasing order of complexity) until convergence is achieved: heterogeneous Toeplitz, heterogeneous first-order autoregressive, autoregressive, heterogeneous compound symmetry, compound symmetry, and variance components. The first structure yielding convergence will be used as the primary analysis. The Kenward and Roger method for calculating the denominator degrees of freedom for tests of fixed effects will be used.

The efficacy comparisons for this MMRM model will be based on the treatment difference vs. placebo estimated at Week 15 using least-squares means. Their point estimates, standard errors, and two-sided 90% CIs will be reported.

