### **9.2.1. Analysis of the Primary Endpoint**

The primary analysis will be conducted on the primary endpoint, the change from baseline in the MDS-UPDRS score Part III at Week 15, based on the FAS population. The primary analysis will utilize a restricted maximum likelihood (REML)-based mixed model for repeated measures (MMRM). The response variable in the model will be the change from baseline to each post baseline visit, and the following fixed effects will be included in the model:

- Treatment (with 2 levels: PF-06649751 and placebo), a categorical factor.
- Visit, a categorical factor.
- Treatment-by-visit interaction.
- Baseline MDS-UPDRS score Part III, a continuous covariate.
- Baseline-by-visit interaction.
- Geographic region as appropriate.

An unstructured variance-covariance structure will be used to model the within-subject errors. In the unlikely event that the computational algorithm fails to converge, the following structures will be executed in the order specified (essentially in decreasing order of complexity) until convergence is achieved: heterogeneous Toeplitz, heterogeneous first-order autoregressive, autoregressive, heterogeneous compound symmetry, compound symmetry, and variance components. The first structure yielding convergence will be used as the primary analysis. The Kenward and Roger method for calculating the denominator degrees of freedom for tests of fixed effects will be used.

The efficacy comparisons for this MMRM model will be based on the treatment difference vs. placebo estimated at Week 15 using least-squares means. Their point estimates, standard errors, and two-sided 90% CIs will be reported.

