#### 6.4. Subset Analyses

The primary endpoint will also be analyzed respectively for subset of subjects:

- in different geographic regions;
- concomitant Parkinson's Disease medication=NO/YES at randomization;
- Subjects with prior dopaminergic anti-PD med exposure;
- Level of subjects' maintenance doses (<3 mg or ≥3 mg).

Only subgroup that has ≥10% of total subjects will be analyzed. The MMRM analysis (See [Section 5.2.2.1](#)) will be performed and similar reporting results as described in [Section 6.1.1](#) will be presented for each of the subset analyses.

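### Minor: the covariance fallback list for the primary model breaks its own order of complexity, trying AR(1) before heterogeneous compound symmetry, and ends in variance components

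*SAP*

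**What the plan says.** The primary analysis is an MMRM on change from baseline in MDS-UPDRS Part III. SAP 5.2.2.1 starts from the fullest structure: "An unstructured variance-covariance structure will be used to model the within-subject errors". The fallback has a single trigger: "In the unlikely event that the computational algorithm fails to converge, the following structures will be executed in the order specified". The list is "heterogeneous Toeplitz, heterogeneous first-order autoregressive, autoregressive, heterogeneous compound symmetry, compound symmetry, and variance components", and Protocol 9.2.1, which carries the same list, describes its order as "essentially in decreasing order of complexity". Selection is mechanical: "The first structure yielding convergence will be used as the primary analysis". Both documents use Kenward-Roger degrees of freedom, and neither names a robust standard error for a restricted structure.

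The quantity at stake is the Week 15 contrast: "The efficacy comparisons for this MMRM model will be based on the treatment difference vs. placebo estimated at Week 15 using least-squares means". SAP Appendix 1 lists the missing-data method for this analysis as observed cases. SAP 6.4 sends the subset analyses through the same model, with the limit "Only subgroup that has ≥10% of total subjects will be analyzed".

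**The concern.** The stated principle is to give up as little flexibility as possible at each step. The list departs from it once: it drops to a structure with one variance for all visits and then returns to one with a separate variance at each visit. Because the first structure to converge becomes the primary analysis, AR(1) would be adopted without heterogeneous compound symmetry being tried.

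Two things would be at stake if the list were followed that far. First, a common variance pools all visits, so the Week 15 standard error reflects the average spread and not the spread at Week 15. Kenward-Roger does not repair a wrong covariance structure. Second, the validity of an observed-case MMRM under missing-at-random dropout comes from the within-subject covariance. Variance components, read in the usual way as a residual structure with one variance and no correlation, removes that link and turns Week 15 into an available-case comparison.

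**Working it through.** **Inputs from the documents.** Post-baseline Part III visits: 4, 6, 8, 10, 12 and 14 (Protocol, Schedule of Activities), so t = 6. From Protocol 9.1: SD 8.4; 34 evaluable per arm; 44 per arm randomized; 23% loss; C1 requires an estimate of at least 3.6; C2 is one-sided 5%; stated pass probabilities 81% (true effect 5.4) and 4% (true effect 0).

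**Assumed, because the documents do not give them.** SDs by visit, correlations between visits, and the dropout mechanism.

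**1. The plan's own figures.** SE = 8.4 × √(2/34) = 2.037, and 1.645 × SE = 3.351. The pass threshold is max(3.6, 3.351) = 3.6.
- True effect 5.4: 1 − Φ((3.6 − 5.4)/2.037) = 81.2%.
- True effect 0: 1 − Φ(3.6/2.037) = 3.9%.
- 44 × 0.77 = 33.9, or about 34.

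The stated figures are reproduced.

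**2. Parameter counts at t = 6, in the written order.**

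| Structure | Formula | Parameters |
|---|---|---|
| Unstructured | t(t+1)/2 | 21 |
| Heterogeneous Toeplitz | 2t − 1 | 11 |
| ARH(1) | t + 1 | 7 |
| AR(1) | 2 | 2 |
| Heterogeneous compound symmetry | t + 1 | 7 |
| Compound symmetry | 2 | 2 |
| Variance components | 1 | 1 |

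The sequence rises once, from 2 to 7. Swapping those two entries and stopping at compound symmetry gives 21, 11, 7, 7, 2, 2, which never rises.

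**3. Standard error under a common variance.** With complete data, the ratio of model SE to true SE at Week 15 is approximately the root-mean-square SD over visits divided by the Week 15 SD.

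| Assumed SD path | Pooled SD | Ratio | 90% CI coverage |
|---|---|---|---|
| Flat 8.4 | 8.40 | 1.00 | 90.0% |
| 7 rising to 8.4 | 7.71 | 0.918 | 86.9% |
| 6 rising to 8.4 | 7.25 | 0.863 | 84.4% |
| 5 rising to 8.4 | 6.80 | 0.81 | 81.7% |
| 9.8 falling to 8.4 | 9.11 | 1.085 | 92.6% |

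A simulation of the repeated-measures model (800 trials per scenario, 44 per arm, about 23% random dropout, no Kenward-Roger adjustment) agrees. For AR(1), the ratio of model SE to empirical SE was 1.05 (flat), 0.81 (5 to 8.4; coverage 80.5%) and 1.14 (falling). Heterogeneous compound symmetry gave 1.04, 1.02 (coverage 91.0%) and 1.04.

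**4. Bias.** Under random dropout no structure showed clear bias (Monte Carlo SE 0.07). Under an assumed outcome-related dropout that differs by arm, the bias in units was:

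| Scenario | Unstructured | ARH(1) | AR(1) | Het. CS | CS | Variance components |
|---|---|---|---|---|---|---|
| Flat SD, AR correlation | +0.01 | 0.00 | 0.00 | −0.30 | −0.23 | +1.14 |
| Rising SD, AR correlation | +0.08 | +0.07 | +0.34 | −0.21 | +0.34 | +1.23 |
| Rising SD, CS correlation | +0.14 | +0.84 | +0.96 | +0.13 | +0.57 | +1.43 |

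**5. Effect on the decision.**
- SE too small by the 0.81 ratio: 1.645 × SE becomes 3.351 × 0.81 = 2.71. C1 still sets the threshold at 3.6, so 81%/4% stands.
- SE too large by 1.085: 3.351 × 1.085 = 3.636. C2 now binds, and the pass probability at 5.4 is 1 − Φ((3.636 − 5.4)/2.037) = 80.7%.
- A bias of 1.2 units would matter more: 1 − Φ((3.6 − 1.2)/2.037) = 12% at no effect if it favours the drug, or 1 − Φ((3.6 − 4.2)/2.037) = 62% at 5.4 if it goes against it.
- C2 binds unaided only above SD = 3.6/(1.645 × √(2/34)) = 9.02.

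**6. How likely the list is to be reached.** In a rough check of 86 simulated datasets with 88, 24, 14 or 9 subjects and 23% dropout, the chain always stopped at unstructured, heterogeneous Toeplitz or ARH(1).

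**The case against.** The strongest reply is that this is one transposed step in a contingency the plan itself calls unlikely. The wording qualifies the order as only essentially decreasing, and the list can be read as grouped by correlation family: Toeplitz and autoregressive first, compound symmetry second. It is fully pre-specified and leaves the analyst no discretion. Nor is heterogeneous compound symmetry always better, since it was itself biased by −0.2 to −0.3 units when the true correlation was autoregressive. Deleting variance components also removes the last resort.

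Most of this stands, and it is why the point is minor. It does not remove the inconsistency: the stated principle is complexity, not family, and a step from 2 parameters up to 7 is not a decrease. As to the last resort, compound symmetry has only two parameters and is a reasonable place to stop, whereas independence gives up the property for which an MMRM is used.

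A reader might infer from SAP 6.4 that small subsets would be pushed down to AR(1): 10% of 88 is 8.8, so 9 subjects qualify. Nine subjects are few for a 6 × 6 unstructured matrix, but the rough check did not reach AR(1) even at that size. C1 and C2 are set for the overall comparison, not for subsets. Whether a 9-subject fit is informative is a question about the 10% limit, not about this list.

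**Conclusion.** The list is out of its stated order at one step and ends in independence, in both documents. That much follows from the text and from counting parameters; the reading of variance components as independence is the usual one, but the documents do not define it.

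The consequences are conditional. Unstructured, heterogeneous Toeplitz and ARH(1) must all fail first. After that, the direction of the standard-error problem depends on how variance changes over visits, and bias needs dropout that depends on outcome and differs by arm. A reader might infer that the list makes the Week 15 interval too narrow, or tilts the result toward the drug. The documents do not support either: they give one SD and no visit-specific SDs or correlations, and the sign of any bias comes from the dropout mechanism assumed. At SD 8.4 with 34 per arm, a too-small standard error alone leaves the 81%/4% unchanged, although the reported 90% CI would still be wrong.

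Limits of the check: the simulation used model-based standard errors, its unstructured fits all gave usable estimates but convergence flags were not inspected, and other software may behave differently. The reordering restores the stated principle; it does not make AR(1) or compound symmetry safe if they are reached.

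**What to change.** In SAP 5.2.2.1 and Protocol 9.2.1, reorder the fallback list to heterogeneous Toeplitz, ARH(1), heterogeneous compound symmetry, AR(1), compound symmetry. Delete variance components, so that compound symmetry is the last fallback.

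The cost is a wording change in two documents, made before unblinding so that the order cannot be linked to results. It needs no extra data or subjects and has no effect when the unstructured model converges.

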### 5.2.3. Analyses for Categorical Data

Categorical data (CCI) will show the number and percentage of subjects for each category and include mean/median descriptive statistics similar to the continuous data (See [Section 5.2.2](#)). Analysis of the categorical data will use Cochran-Mantel-Haenszel methods, where row-mean-score-difference tests use ridit scores that yield nonparametric analyses.

### 5.3. Methods to Manage Missing Data

For the analysis of safety endpoints, the sponsor data standard rules for imputation will be applied (eg, partial dates for AEs and concomitant medications will be imputed according to Pfizer standard algorithms).

For scales used in this study, scores will be imputed according to the imputation rules and algorithms for missing component scores that are provided in the data standard documents, or scale documentation. Details are included for each endpoint in [Section 3](#).

If baseline measures are missing, the last values prior to study treatment, provided that the data is collected on or after the screening visit will be used. This information is used as a reference for the measurements and observations made subsequent to the start of study treatment.

CCI [REDACTED]

### 6. ANALYSES AND SUMMARIES

Both the FAS and PPAS populations will be used in the analyses of the primary efficacy endpoint, with the FAS being primary. For all other efficacy endpoints, only the FAS analysis set will be utilized.

## 6.1. Primary Endpoint(s)

### 6.1.1. MDS-UPDRS score Part III

#### 6.1.1.1. Primary Analysis

##### Endpoints: MDS-UPDRS Part III total score

- Analysis time points: Week 15.
- Analysis population (method of imputation for missing data): FAS (See [Section 3.1](#)).
- Analysis methodology: Change from baseline will be analyzed using the MMRM Analysis (See [Section 5.2.2.1](#)).
- Supporting objective and Decision rule: Primary Objective (See [Section 2.1.1](#)).

##### Reporting results:

- Raw data: The sample size, mean, standard deviation, median, minimum and maximum at baseline and post-baseline visits will be presented for each treatment arm.
- Change from baseline: The sample size, mean, standard deviation, median, minimum and maximum will be presented for each treatment arm. The point estimate, 90% confidence interval for the point estimate, difference from the placebo for each pair of treatment groups and the corresponding 90% confidence interval will be presented.

##### Figures

- Vertical bar chart of LS means and 90% confidence intervals at Week 15.
- Change from baseline time profile per MMRM for each treatment group.
- Empirical cumulative distribution function showing % of subjects with change from baseline  $\leq$  cutoff value at Week 15 by treatment group with missing values assigned to the worst outcome.

#### 6.1.1.2. Sensitivity/Robustness Analyses

To support the interpretation of the primary analysis the following analyses will be performed:

##### Endpoint: MDS-UPDRS Part III total score

- Analysis time points: Week 15.
- Analysis populations (method of imputation for missing data): PPAS (See [Section 3.1](#)).

- Analysis methodology: Change from baseline will be analyzed using the MMRM Analysis (See [Section 5.2.2.1](#)).

**Reporting results:**

- Raw data: The sample size, mean, standard deviation, median, minimum and maximum at baseline and post-baseline visits will be presented for each treatment arm.
- Change from baseline: The sample size, mean, standard deviation, median, minimum and maximum will be presented for each treatment arm. The point estimate, 90% confidence interval for the point estimate, difference from the placebo for each pair of treatment groups and the corresponding 90% confidence interval will be presented.

**6.2. Secondary Endpoint(s)**

Safety and tolerability of PF-06649751 will be described under the safety summaries and analyses (See [Section 6.6](#)).

CCI [REDACTED]

[REDACTED]

[REDACTED]

[REDACTED]

[REDACTED]

- [REDACTED]
- [REDACTED]
- [REDACTED]
- [REDACTED]

[REDACTED]

- [REDACTED]

090177e18fca9a96\Approved\Approved On: 19-Nov-2018 07:48 (GMT)

• CCI [Redacted]

[Redacted]

• [Redacted]

• [Redacted]

• [Redacted]

[Redacted]

• [Redacted]

• [Redacted]

• [Redacted]

• [Redacted]

[Redacted]

• [Redacted]

• [Redacted]

CCI [Redacted]

[Redacted]

090177e18fca9a96\Approved\Approved On: 19-Nov-2018 07:48 (GMT)

CCI [Redacted]

- | [Redacted]
- | [Redacted]
- | [Redacted]
- | [Redacted]

[Redacted]

- | [Redacted]

[Redacted]

[Redacted]

[Redacted]

- | [Redacted]
- | [Redacted]
- | [Redacted]
- | [Redacted]

[Redacted]

- | [Redacted]

[Redacted]

- | [Redacted]

#### 6.4. Subset Analyses

The primary endpoint will also be analyzed respectively for subset of subjects:

- in different geographic regions;
- concomitant Parkinson's Disease medication=NO/YES at randomization;
- Subjects with prior dopaminergic anti-PD med exposure;
- Level of subjects' maintenance doses (<3 mg or ≥3 mg).

Only subgroup that has ≥10% of total subjects will be analyzed. The MMRM analysis (See [Section 5.2.2.1](#)) will be performed and similar reporting results as described in [Section 6.1.1](#) will be presented for each of the subset analyses.

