## Study Design

The study has a randomized, double-blind, placebo-controlled, flexible-dose design. Approximately 88 subjects from approximately 30 centers in up to 5 countries will be randomized to 2 treatment groups (PF-06649751 or placebo) in a 1:1 ratio using a central randomization system. Each subject will undergo 15 weeks of double-blind treatment (including 9 weeks of Dose Optimization Period and 6 weeks of stable dosing during the Dose Maintenance Period). During the initial up titration, subjects will gradually increase the dose of investigational product at weekly intervals, as tolerated, until Parkinsonian symptoms are optimally controlled. Investigational product will be self-administered once daily. The target dose range for PF-06649751 is 3 mg to 15 mg once daily (Stage 4 – Stage 8 in [Table 2](#)). Adjustments to the up-titration schedule are permitted during the Dose Optimization Period based on clinical judgment to mitigate adverse events or symptoms of suspected dopaminergic overstimulation.

The 15 weeks of double-blind treatment will be preceded by a 30 day screening period. There will be an additional follow-up period of 28 days following discontinuation of investigational product, for total study duration of up to 23 weeks.

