Contraception check (Serum Pregnancy)/FSH Test 	X																
Serological Testing 	X																
Urine drug screening 	X	X															
Safety laboratory 	X	X 					X				X		X		X	X 	
CCI		█							█	█	█	█	█				█
CCI			█	█	█	█									█		
CCI			█		█	█	█				█		█		█		
ECG 	X	X	X	X	X		X		X		X		X		X	X	
Supine and standing blood pressure and heart rate	X 	X	X	X	X		X		X		X		X		X	X	
Columbia Suicidality Severity Rating Scale (C-SSRS) 	X	X	X	X	X		X		X		X		X		X	X	
Patient Health Questionnaire (PHQ-8)	X																
Questionnaire for Impulsive-Compulsive Disorders in Parkinson's Disease – Rating Scale (QUIP-RS)		X					X				X				X		
Inclusion/exclusion criteria verification	X	X															
Randomization		X															

090177e18fca9a98\Approved\Approved On: 19-Nov-2018 07:50 (GMT)

Visit Identifier	Screening Visit	Dose Optimization Period										Dose Maintenance Period				Follow Up Period	
		Visit 1	Visit 2	Visit 3	Visit 4	Visit 5	Visit 6	Visit 7	Visit 8	Visit 9	Visit 10	Visit 11	Visit 12	Visit 13	Visit 14 or Early Termination	Visit 15	Visit 16
Protocol Activity	D -30 to -2	D -1/ RAND	D 7 +3	D 14 +3	D 21 +3	D 28 +3	D 35 +3	D 42 +3	D 49 +3	D 56 +3	D 63 ±3	D 70 ±3	D 84 ±3	D 98 ±3	D 105 -3	D 119 ±3	D 133 ±3
		Wks 1 – 9										Wk 10	Wk 12	Wk 14	Wk 15	Wk 17	Wk 19
Subject training on management of investigational product and dosing diary		X			X						X						
Investigational product accountability			X	X	X		X		X		X		X		X		
Dosing compliance verification via phone 						X		X		X		X		X			
Subject investigational product dosing diary 		X	→	→	→	→	→	→	→	→	→	→	→	→	X		
Decision tree review 			X	X	X	X	X	X	X	X	X						
Dispensing of Investigational product		X	X	X	X		X		X		X		X				
Administration of Investigational product 		X 	→	→	→	→	→	→	→	→	→	→	→	→	X		
MDS-UPDRS III 	X	X			X		X		X		X		X		X		
CCI	■	■	■	■	■	■					■		■		■		
CCI		■									■				■		
		■									■				■		
		■									■				■		
											■				■		
CCI		■									■				■		
		■									■				■		

090177e18fca9a98\Approved\Approved On: 19-Nov-2018 07:50 (GMT)

Visit Identifier	Screening Visit	Dose Optimization Period										Dose Maintenance Period				Follow Up Period	
		Visit 1	Visit 2	Visit 3	Visit 4	Visit 5	Visit 6	Visit 7	Visit 8	Visit 9	Visit 10	Visit 11	Visit 12	Visit 13	Visit 14 or Early Termination	Visit 15	Visit 16

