**9. APPENDICES**

**Appendix 1. SUMMARY OF EFFICACY ANALYSES**

Endpoint	Analysis Set	Statistical Method	Missing Data	Interpretation
MDS-UPDRS Parts III, Week 15	FAS	MMRM	OC	Primary Analysis
MDS-UPDRS Parts III, Week 15	FAS-by geographic region	MMRM	OC	Subset Analysis*
MDS-UPDRS Parts III, Week 15	FAS-by concomitant Parkinson's Disease medication at randomization (NO/YES)	MMRM	OC	Subset Analysis*
MDS-UPDRS Parts III, Week 15	FAS-by prior dopaminergic anti-PD med exposure (NO/YES)	MMRM	OC	Subset Analysis*
MDS-UPDRS Parts III, Week 15	FAS-by level of subjects' maintenance doses (<3 mg or ≥3 mg)	MMRM	OC	Subset Analysis*
MDS-UPDRS Parts III, Week 15	PPAS	MMRM	OC	Sensitivity Analysis
MDS-UPDRS Parts III, All Other Visits	FAS	MMRM	OC	Secondary Analysis
MDS-UPDRS Parts I, II, IV, and total score, All Visits	FAS	MMRM	OC	Secondary Analysis
CCI [REDACTED]	FAS	MMRM	OC	CCI [REDACTED] Endpoints
[REDACTED]	FAS	CMH	LOCF	CCI [REDACTED] Endpoints

\*Only subgroups that have ≥10% of total subjects will be analyzed.

090177e18fca9a96\Approved\Approved On: 19-Nov-2018 07:48 (GMT)

CCI

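### Subset MMRMs are refitted separately in groups as small as 9 subjects, where the unstructured model usually cannot be estimated, and no treatment-by-subgroup term is planned

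*SAP*

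**What the plan says.** SAP 6.4 introduces the subset analyses with "The primary endpoint will also be analyzed respectively for subset of subjects". It lists four groupings: geographic region, concomitant Parkinson's medication at randomisation, prior dopaminergic exposure, and maintenance dose below versus at or above 3 mg. The only condition is "Only subgroup that has ≥10% of total subjects will be analyzed", and SAP Appendix 1 repeats it in a footnote: "Only subgroups that have ≥10% of total subjects will be analyzed".

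Each subset uses the model of SAP 5.2.2.1. That model has treatment, visit, treatment-by-visit, baseline score, "Baseline-by-visit interaction", and main effects for region and concurrent PD medication. On the covariance: "An unstructured variance-covariance structure will be used to model the within-subject errors". If the fit does not converge, which the SAP regards as unlikely, six simpler structures are tried in a fixed order and the first to converge is used.

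The SAP sets no per-arm minimum, gives no reduced model for subsets, and plans no treatment-by-subgroup interaction. It does not say what happens to a stratification factor that is constant within a subset, and it does not define convergence.

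**The concern.** A rule written for an 88-subject analysis is carried unchanged into groups a tenth of that size. The unstructured model has a hard minimum number of subjects with Week 15 data, and the 10% floor sits at or below it. Near the floor, failure of the specified model is the expected outcome, not the unlikely event that SAP 5.2.2.1 provides for. Two levels of one factor, such as a large and a small region, could then be compared under different covariance models.

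The second problem does not depend on size. Separate fits give one treatment difference per level but no estimate, with an interval, of how far the levels differ. That is the question a subset analysis is normally read to answer.

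**Working it through.** **Inputs**
- 88 randomised, 1:1, up to 5 countries (Protocol Summary, Study Design; Protocol 9.1).
- 23% assumed not to complete or not to optimise the dose; SD 8.4; criterion C1 of 3.6 units; true effect 5.4 (Protocol 9.1).
- Six post-baseline Part III assessments, at Visits 4, 6, 8, 10, 12 and 14 (Protocol Schedule of Activities).
- Model terms from SAP 5.2.2.1.

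**Reproducing the plan's figures.** SE = 8.4 × √(2/34) = 2.037. The C2 cut-off is 1.645 × 2.037 = 3.35, so C1 (3.6) binds. P(pass | 5.4) = Φ((5.4 − 3.6)/2.037) = 81.2% (stated 81%). P(pass | 0) = 1 − Φ(3.6/2.037) = 3.9% (stated 4%). 34/0.77 = 44.2 per arm (stated 44). The design inputs are consistent.

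**The floor.** 0.10 × 88 = 8.8, so 9 subjects.

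**Model size.** Unstructured covariance for six visits: 6 × 7/2 = 21 parameters. Intercept, treatment and baseline at each visit: 3 × 6 = 18. With one stratum term the total is 40, against at most 9 × 6 = 54 observations.

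**Minimum for estimability.** Under monotone dropout, the Week 15 part of the unstructured likelihood is a regression of the Week 15 change on intercept, treatment, baseline and the five earlier changes: 8 coefficients. A positive residual variance needs at least 9 subjects with Week 15 data. Each stratum parameter left in the model (k of them) adds one, so the minimum is 9 + k. Region subsets keep PD medication (k = 1). PD-medication subsets keep region (k = number of levels − 1). Prior-exposure subsets keep both.

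**Probability of reaching it.** P(X ≥ 9 + k) with X ~ Binomial(N, 0.77). For N = 9 and k = 0 this is 0.77⁹ = 9.5%.

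| N | k = 0 | k = 1 | k = 2 | k = 4 (e.g. five regions) |
|---|---|---|---|---|
| 9 | 9.5% | 0% | 0% | 0% |
| 10 | 29% | 7% | 0% | 0% |
| 12 | 71% | 46% | 20% | 0% |
| 14 | 92% | 80% | 59% | 13% |
| 16 | 98% | 95% | 86% | 48% |
| 20 | >99% | 99.8% | 99% | 93% |
| 24 | >99% | >99% | >99% | 99.7% |

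**Sensitivity to retention.** At N = 9 and k = 0: 23% with 85% retention, 39% with 90%. At N = 12 and k = 1: 74% and 89%. At N = 9 and k = 1 it is 0% at any retention.

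**Check by simulation.** REML fits at 77% retention (assumed serial correlation 0.7, SD 8.4, monotone dropout) gave a usable unstructured estimate in 6/40 data sets at N = 9, 30/40 at N = 12 and 39/40 at N = 14 with k = 0. With k = 1 the counts were 0/30 at N = 9, 9/30 at N = 12, 27/30 at N = 14 and 29/30 at N = 16. With k = 1, N = 9 and no dropout, 0/15 were usable. Heterogeneous AR(1) converged in every data set whose design matrix had full rank.

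**Precision.** For 4 versus 5 complete subjects fitted alone, the 90% half-width is t(0.95, 7) × 8.4 × √(1/4 + 1/5) = 1.895 × 5.635 = 10.7 units. With the SD pooled over the FAS (about 80 df, t = 1.664) it is 9.4. At 10 per arm, pooled, it is 1.664 × 8.4 × √(2/10) = 6.3.

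**The case against.** The strongest reply is that the documents give neither subgroup sizes nor the number of regions, so no subset is shown to sit near the floor. For a two-level factor at most one level can be that small. This stands and limits the scope. A reader might infer that every subset above 10% is affected, but the table does not support that.

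A reader might also infer that the covariance model is picked arbitrarily. It is not: SAP 5.2.2.1 fixes the order and the selection rule. What remains is that the chosen structure can differ between levels, and that a singular fit reported as converged is not covered.

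It is tempting to go further and claim that standard errors would be too small because fits land on equal-variance AR(1). That structure is reached only after heterogeneous Toeplitz and heterogeneous AR(1) have both failed, and the latter converged in every full-rank simulated data set. Severe arm imbalance is likewise not established in general. Protocol 4.3 blocks randomisation by region, and the SAP treats PD medication as a stratification factor too, so unrestricted allocation is the wrong reference for those groupings.

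The 23% includes failure to optimise the dose, and Protocol 6.5 keeps subjects who stop treatment in follow-up. It is therefore an upper figure for missing Week 15 data. Wide intervals in small subsets are mainly a matter of sample size: pooling moves 10.7 only to 9.4.

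Finally, no decision rule uses the subsets. Criteria C1 and C2 attach to the overall comparison. That lowers the stakes but leaves the method as it is.

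**Conclusion.** The point holds for small subsets and, as regards the missing interaction, for all of them. At 9 to about 11 subjects the specified unstructured model usually cannot be estimated. At 12 to 14 it depends on how many stratum terms remain. From about 16 subjects with one stratum term, or 20 to 24 with five region levels, it usually can. At any size, the plan yields no estimate of whether the effect differs between levels.

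This rests on 23% as an upper figure for missing Week 15 data, monotone dropout, an assumed number of region levels (two to five), and total subjects meaning the 88 randomised. If it means the FAS, the floor is no higher.

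A reader might take this as a threat to the primary result. It is not: the primary MMRM is fitted on the whole FAS. This is a worthwhile, inexpensive improvement to the supporting analyses.

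A minor side point: the fallback list is described as "essentially in decreasing order of complexity", yet for six visits AR(1) (2 parameters) precedes heterogeneous compound symmetry (7). Heterogeneous AR(1), also with 7, comes before both, so the practical effect is likely to be small.

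**What to change.** In SAP 6.4 and Appendix 1, for each baseline factor (region, concomitant PD medication, prior dopaminergic exposure), fit one MMRM on the whole FAS. Add to the SAP 5.2.2.1 model the subgroup main effect where it is not already there, subgroup-by-visit, treatment-by-subgroup and treatment-by-subgroup-by-visit. Report the Week 15 treatment difference per level and the interaction contrast, each with a 90% CI.

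Even with five region levels, the Week 15 regression then has 3 + 5 + 4 + 4 + 1 = 17 coefficients, against about 0.77 × 88 = 68 subjects with Week 15 data. Estimability of the covariance is no longer in doubt.

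Replace the 10% rule with a stated minimum per arm for displaying a level. The number is the sponsor's choice. At 10 per arm the half-width is still about 6 units, so small levels should be read as descriptive. The maintenance-dose split is formed after randomisation and is outside this proposal.

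If the fallback list is reordered, make the same change in Protocol 9.2.1, which carries the same list.

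The cost is SAP wording and modest programming, with no new data. The statistical price is a covariance matrix assumed common to all levels of a factor.
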